1. Active or Sham CES Administration: Participants will be asked to continue sitting and relaxing in the chair and the electrode cable (still attached to their earlobes) will be connected to a different CES device. Two types of CES devices will be used: an Active device or a Sham device. The Sham devices are manufactured by EPII and look and behave exactly like the Active devices, however they do not actually send any electrical current to the electrodes. The two versions of the devices will be coded as devices A and B, and neither the experimenter nor participant will know which is Active and which is Sham; only the Principal Investigator will keep the key to decode whether the device is Active or Sham, to be revealed only during data analysis (or to a medical professional if there is an adverse event). The experimenters and participants will only know which coded device (device A or B) to use during CES sessions. In both conditions, the device will be powered on and set to the intensity identified during the CES Individualized Thresholding phase, and a countdown timer (displayed on the device screen) will begin.

After the 20 minutes of stimulation have elapsed, the device will automatically turn off. Immediately after the 20-minute CES administration, participants will complete the STAI-S questionnaire a second time, and the CES side effects questionnaire.

2. CES Secondary Administration: If a participant answer is ≥ 3 to one or more questions on the CES side effects questionnaire (in *both* the “presence and intensity” and the “relation to stimulation” sections), we will follow the manufacturer’s guidelines to administer additional CES until symptoms subside. According to the manufacturer’s internal research (derived from an analysis of over 10,000 CES sessions), brief secondary CES administrations can help

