alleviate most side effects in most circumstances. Specifically, we will provide successive 5-minute secondary CES administrations at the individualized intensity. After each secondary CES administration, there will be a 1-minute break when the participant will again complete the CES side effects questionnaire. The successive 5-minute CES administrations with interleaved CES side effects questionnaire will be repeated up to twice, or until the negative sensations subside (i.e., all ratings ≤ 3), whichever occurs first. The number of secondary CES administrations necessary to resolve vestibular sensations or anxiety (i.e., 1 or 2) will be recorded by the experimenter. If the participant's reported symptoms do not subside with secondary CES administration, and this occurs for two consecutive CES sessions, they will be withdrawn from the study. Participants will then be dismissed until their next session.

Below is an example schedule for a CES session:

0800-0810	Questionnaires (daily checklist, STAI-S)
0810-0830	CES Administration
0830-0835	Side Effects Questionnaire
0835-0850	Secondary CES Administration (as necessary)
0850-0900	STAI-S Questionnaire
0900	Dismissal

Our goal is to have each participant complete a total of 20 CES sessions, though we do expect some attrition (see Section 3.0). We will prioritize the number of sessions (i.e., reaching 20) over the duration of the study; for example, some participants may complete the 20 sessions study in a 5-week period (rather than 4-week period) due to scheduling issues. We will allow up to 6 weeks to complete the study; if the 20 sessions are not completed in 6 weeks, the participant will be removed from the study. Variability in completion time (i.e., inter-session lag) will be recorded and used as a covariate in statistical analyses.

At the end of the final CES session (session 20), participants will complete the Final CES Session Questionnaire (Appendix A) to assess whether our blinding was successful, and their opinions about CES.

Final Testing Day: Follow-up

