The final testing day will serve as the follow-up session to assess whether 20 sessions of Active (versus Sham) CES will impart any changes to the biochemical, physiological, affective, or behavioral responses to stress induction. This session will be held at approximately the same time of day as the thresholding and baselining session, within 5 days of the last daily CES session. The procedures for this session will precisely match the thresholding and baselining session but without the thresholding phase. After completing the final testing day, participants will have completed the study.

Data Analysis

We will analyze data from our biochemical, physiological, affective, and behavioral measures using Generalized Estimating Equations (GEEs) and/or Analyses of Variance (ANOVAs) to examine changes over the 20 CES sessions, changes from baseline to follow-up, and changes due to Active versus Sham CES. An effect will be deemed statistically significant if the likelihood of its occurrence by chance is $p < 0.05$; to reduce the likelihood of a Type I error, any follow-up comparisons (e.g., t-tests) will use a Bonferroni-corrected alpha criterion.

6.1 Additional Safeguards for Special Populations:

This research is funded by the Department of Defense, and the funding agency is interested in how military personnel respond to CES administration; for that reason, we will prioritize the recruitment of military personnel, and secondarily recruit from civilian populations as required to fulfill our sample size goal.

When recruiting military personnel to participate in this research, we will conform to additional safeguards for the protection of human subjects outlined in DoD Instruction (DoDI) 3216.02. These include additional safeguards to protect participants who may be more vulnerable to coercion or undue influence.

7.0 Investigational Medical Devices:

For the CES sessions, we will be using the Alpha-Stim AID cranial electrotherapy stimulator (CES) medical device, which is an FDA cleared, handheld medical device used for the treatment of anxiety, insomnia, and depression (i.e., AID; see Appendix D).

Because our study is using the device with healthy participants, the device is being used off-label in a manner that is for *investigational use only*. As detailed in the Informed Consent Form, this means that the device is being used in a study examining its safety or effectiveness, and not for the treatment, diagnosis, or prevention of any disorder.

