more objective assessment, we reviewed some CES studies that were not associated with (i.e., funded by, conducted by) the manufacturer. In one of the largest CES studies to date, none of the 115 participants (N = 60 in Active CES group) reported any side effects with six weeks of daily (one hour per day; 0.5Hz at 100 μ A) CES administration (Barclay & Barclay, 2014). In another similarly designed study using CES at 0.5Hz and 300 μ A, 3 of the 12 participants dropped out of the study due to mild side effects (2 with dizziness, 1 with headache) (Bystritsky et al., 2008). In another study, participants receiving Active CES treatment for 2 weeks (20 minutes per day; N = 7; 2mA at mixed frequencies) showed similarly low rates of reported side effects as the Sham CES group (McClure et al., 2015). In our own recent study (0.5Hz, 100 μ A), reports of side effects were also no more frequent in the Active versus Sham CES group (Brunye et al., 2022). Given these results, we estimate that the rate of side effects with our proposed design will be very low (i.e., less than 25%), especially given our individualized daily thresholding procedure. See Study Withdrawal Guidelines (Section 3.0) for details. Participants will be informed of the risk of CES side effects, and that they can opt-out at any time due to discomfort with CES administration, in the Informed Consent Form.

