Cognitive & Affective Responses to CES. To evaluate the cognitive and affective responses to CES, we will use mixed ANOVAs to assess the effect of CES Group (2: Active, Sham) and Session (2: Baseline, Follow-up) on each of four cognitive outcome measures, and one affective outcome measure. Cognitive measures include RMT overall accuracy, SOT absolute angular direction error, SOT absolute distance estimate error, DMT discriminability (d'), and DMT response criterion (c). Affective measures include STAI-S scores, and we will use a mixed ANOVA to assess the effect of CES Group (2: Active, Sham), Session (2: Baseline, Follow-up), and Time (pre-task, 0-min, 20-min, 40-min, 60-min post-task).

Mixed ANOVAs will be conducted using package *rstatix* (ver. 0.7.0; Kassambara, 2023) in R (ver. 4.1.2). Mixed ANOVA assumptions will be checked using package *rstatix* (ver. 0.7.0; Kassambara, 2023) in R (ver. 4.1.2). Extreme outliers will be identified, removed, and mean imputed. Normality will be assessed with Shapiro-Wilk Normality Test; non-normal data will be log-transformed. Homogeneity of variance will be assessed with Levene's Test and confirmed all groups had the same or similar variance. Mauchly's test of sphericity will be automatically conducted and corrected for in the mixed ANOVAs analysis.

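### No by-arm summary of CES side effects or secondary stimulation is planned, and the withdrawal rule destroys the data of those dismissed for CES intolerance

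*Protocol*

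**What the plan says.** **Collection.** In protocol Section 6.0 (The CES Sessions), the side effects questionnaire follows each 20-minute administration, when "participants will complete the STAI-S questionnaire a second time, and the CES side effects questionnaire". A rating of 3 or more on both the intensity and the relation scales triggers up to two further 5-minute blocks. The questionnaire is repeated each time: "After each secondary CES administration, there will be a 1-minute break when the participant will again complete the CES side effects questionnaire". The blocks are counted: "The number of secondary CES administrations necessary to resolve vestibular sensations or anxiety (i.e., 1 or 2) will be recorded by the experimenter".

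**Dismissal.** Under Sections 3.0 and 6.0, a participant whose symptoms do not subside after secondary CES in two consecutive sessions leaves the study. Section 16.0 then has all data collected before withdrawal destroyed and left out of the analysis.

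**Analysis.** The Data Analysis part of Section 6.0 opens "We will analyze data from our biochemical, physiological, affective, and behavioral measures" and adds no other class of outcome. The SAP contains a manipulation check, six physiological and biochemical outcomes, and "each of four cognitive outcome measures, and one affective outcome measure". It does not mention side effects, secondary CES, adverse events or CES-related dismissals.

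**Other uses of the ratings.** They set the Day 1 threshold, trigger secondary CES and drive dismissal (Sections 3.0 and 6.0). In Section 19.0 the investigator inspects them to check that staff follow the mitigation procedures.

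**The concern.** Section 15.0 lists CES side effects as one of three primary risks and estimates their rate at below 25%. Of the studies it cites, the one closest in frequency and intensity (0.5 Hz, 300 µA) is reported with "3 of the 12 participants dropped out of the study due to mild side effects". This trial uses at least 250 µA and up to 500 µA, against 100 µA in the team's previous study, in healthy volunteers.

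Two gaps combine. First, no by-arm summary is planned even for participants with complete data. Second, the data rule removes the people for whom tolerability was worst, so a summary decided on later could not be put right. At stake is whether the trial can say anything sound about tolerability at this intensity, or set its own rate beside its 25% estimate.

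There is also a link to efficacy. Untabulated secondary blocks leave it unknown how much stimulation the Active arm received.

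**Working it through.** **1. The plan's own figure.** Section 5.2 gives N = 38 for f = 0.47, power 0.80 and alpha 0.05. For a two-group F test the noncentrality is λ = N·f². At N = 38, λ = 38 × 0.2209 = 8.39 and power is 0.805; at N = 37 power is 0.794. So 38 reproduces, and the target of 40 gives 0.826. The sample size is not disputed; it supplies the 20 per arm used below.

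**2. Is there an analysis?** Four places could hold one:
- Protocol 6.0, Data Analysis: four classes of measure, none of them side effects.
- SAP, Manipulation Check and Physiological & Biochemical Responses: AA, HR, CORT and STAI-S, then HR, HRV, RR, tonic PD, AA and CORT.
- SAP, Cognitive & Affective Responses: RMT, SOT and DMT measures, and STAI-S.
- Protocol 19.0: oversight of staff procedures, with no comparison of arms.

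None contains a summary of side-effect ratings, secondary blocks or CES dismissals.

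**3. Volume of data.** In completers there are 40 × 20 = 800 ratings taken straight after stimulation, 400 per arm. Secondary CES adds up to 2 × 5 = 10 minutes to a 20-minute session, which is 10/20 = 50% more.

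**4. Who would be missing.** Section 3.0 expects 40–50% attrition. Reaching 40 complete data sets then needs 40/0.6 = 67 to 40/0.5 = 80 enrolled, so 27 to 40 people do not complete. Some of them fail the threshold on Day 1 and never have a CES session. The documents do not split the rest by reason, so the number lost to CES intolerance is unknown.

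The direction of the bias is known. Everyone dismissed for CES intolerance has, by the dismissal rule, met the event definition at least twice. Removing k such people changes an arm's rate from (x + k)/(20 + k) to x/20. As an illustration, take x = 0 and k = 3. The completers-only result is 0/20, with an upper limit of 17%, which appears to exclude 25%. The all-treated result is 3/23 = 13%, with an upper limit of 34%, which does not.

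**5. What 20 per arm can show.** Exact (Clopper-Pearson) 95% limits are the 0.025 quantile of Beta(x, n−x+1) and the 0.975 quantile of Beta(x+1, n−x).

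| Events | Rate | 95% CI |
|---|---|---|
| 0/20 | 0% | 0 to 16.8% |
| 1/20 | 5% | 0.1 to 24.9% |
| 2/20 | 10% | 1.2 to 31.7% |
| 5/20 | 25% | 8.7 to 49.1% |

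For the Active–Sham difference, the Newcombe interval combines Wilson limits: 11.2 to 46.9% for 5/20, 0 to 16.1% for 0/20, and 0.9 to 23.6% for 1/20.
- 5/20 v 0/20: lower limit 25 − √(13.8² + 16.1²) = 3.8; upper limit 25 + √(21.9² + 0²) = 46.9 points.
- 5/20 v 1/20: lower limit 20 − √(13.8² + 18.6²) = −3.2; upper limit 20 + √(21.9² + 4.1²) = 42.3 points.

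For an assumed 25% on Active and 5% on Sham, power is 0.42 (0.30 with Fisher's exact test). The arm rates are illustrative; the documents give none by arm.

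**The case against.** **The trial has no safety objective.** This is correct. Sections 1.0 and 2.0 contain no safety aim or hypothesis, and Section 7.0 says the intent is to test effectiveness because safety is already documented elsewhere. A reader might infer from the nearby wording about safety or effectiveness that the SAP fails to deliver a stated aim. It does not: that wording explains what investigational use means in the consent form. The omission is explained but not filled.

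**Nothing forbids a report, and the ratings are watched.** Also correct. A reader might infer that the trial will withhold its side-effect data. The documents support only that no by-arm summary is planned. Section 19.0 is monitoring, and it does not preserve the data that Section 16.0 destroys.

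**The other cited evidence is reassuring.** Section 15.0 also reports no side effects among 115 participants at 100 µA, and rates no higher than Sham in the team's own 100 µA study and in a small 2 mA study. That belongs in the picture. Moreover, the 3/12 (25%, exact CI 5% to 57%) is a dropout proportion, not a symptom rate, and should not be set against 5/20 as like with like. Nor do the documents rank intensity as the main change: Section 2.0 gives three primary changes without ordering them.

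**The arms are too small.** In part. It is tempting to say that a 25% Active rate would clearly separate from Sham. The interval excludes zero at 5/20 v 0/20, but a single Sham event removes that. This argues for description with intervals, not for leaving the data unsummarised.

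**Conclusion.** The omission is certain from the text: ratings and secondary blocks are collected, and no by-arm summary is planned. The data rule in Section 16.0 makes it more than a missing table, because analysts following the plan could not later build a sound summary of everyone treated. The plan should be changed, but the point does not touch the sample size or the efficacy analyses.

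The size is modest. A summary at 20 per arm would be descriptive, and only 0 or 1 affected participants out of 20 would place the upper limit below 25%. Even then, a completers-only count would not establish it. These figures assume 20 completers per arm and illustrative event rates. The number dismissed for CES intolerance cannot be estimated from the documents.

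**What to change.** Add a descriptive harms summary to the SAP, by allocated arm, in everyone with at least one Active or Sham CES session:

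1. Number and percentage of participants with at least one session rated 3 or more on both the intensity and the relation scales. Use the rating taken straight after the 20-minute administration and exclude Day 1 thresholding, when everyone receives active current. Give exact 95% CIs and a CI for the Active–Sham difference, with no significance test.
2. Sessions with secondary CES, number of blocks, and total stimulation minutes (device-on time in Sham, which delivers no current).
3. Dismissals for CES intolerance.

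Show the Active rate beside the protocol's 25% estimate.

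Amend Section 16.0 so that side-effect ratings and reasons for dismissal are kept and analysed, as consent and the IRB permit. Where data have already been destroyed, label the ratings as completers only and give dismissal counts by arm if records allow.

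One related inconsistency affects item 3. Section 3.0 treats symptoms as subsided when ratings fall below 3, while Section 6.0 accepts ratings of 3 or less. The two passages must be reconciled before dismissals are counted.

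**Cost.** One SAP paragraph and one or two tables, with no new visits or measurements; a small amendment to Section 16.0 and possibly to the consent form; and wide intervals.

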First, during the individualized baselining phase (part of the Thresholding and Baselining session), if a participant does not reach our minimum CES intensity of 250µA (i.e., a 300µA minimum threshold), they will be dismissed from the study.

Second, during the baseline or follow-up session, if a participant cannot reach the accuracy criterion during the criterial learning tasks within 5 study-test cycles, they will be dismissed from the study.

Third, during the baseline or follow-up session, if a participant cannot tolerate the torso shock (psychologically or physically), we will reschedule their session for a different day. If during two consecutive sessions they cannot tolerate the level 3 intensity, they will be dismissed from the study.

Fourth, at the beginning of any CES session, if the participant answers a 3 or higher (on the scale from 1-4) to any of the Daily Participant Questionnaire items, their session will be rescheduled for a different day. If they report 3 or higher for any of these questions for two consecutive sessions, they will be dismissed from the study.

Fifth, during any CES session, if a participant cannot tolerate the CES administration at their individualized intensity (i.e., answering ≥ 3 to a single item on the “presence and intensity” *and* “relation to stimulation” sections), they will receive secondary CES stimulation as described in the Procedures section (6.0). If their reported symptoms do not successfully subside (i.e., falling below a 3 rating) after the secondary stimulation, and this occurs for two consecutive sessions, they will be dismissed from the study.

Each of these study dismissal criteria are described in more detail in the Procedures section (6.0), and detailed in the Appendix E flowchart.

4.0 Special Populations:

- Children
- Fetuses/Neonates
- Prisoners
- Members of the military
- Non-English speakers
- Those unable to read (illiterate)
- Employees of the researcher
- Students of the researcher

- Adults lacking capacity to consent and/or adults with diminished capacity to consent, including, but not limited to, those with acute medical conditions, psychiatric disorders, neurologic disorders, developmental disorders, and behavioral disorders
- Disadvantaged in the distribution of social goods and services such as income, housing, or healthcare
- Fear of negative consequences for not participating in the research (e.g. institutionalization, deportation, disclosure of stigmatizing behavior)

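### A side-effect rating of exactly 3 in both questionnaire sections has subsided under Protocol Section 6.0 but not under Section 3.0, and it still meets the trigger for secondary CES

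*Protocol*

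**What the plan says.** Three rules in the Protocol act on the same side-effects questionnaire.

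- **Trigger.** Section 6.0, CES Secondary Administration, begins "If a participant answer is ≥ 3 to one or more questions on the CES side effects questionnaire" and requires this in both the intensity section and the relation-to-stimulation section. The fifth withdrawal criterion in Section 3.0 uses the same trigger.
- **Stopping.** Section 6.0 gives 5-minute blocks, each followed by a 1-minute break for the questionnaire, up to a limit "or until the negative sensations subside (i.e., all ratings ≤ 3), whichever occurs first". The limit is two blocks: "The number of secondary CES administrations necessary to resolve vestibular sensations or anxiety (i.e., 1 or 2) will be recorded by the experimenter".
- **Dismissal.** Section 6.0 goes on: "If the participant's reported symptoms do not subside with secondary CES administration, and this occurs for two consecutive CES sessions, they will be withdrawn". It gives no cutoff in that sentence. Section 3.0 has the same two-session rule but does define the term: "If their reported symptoms do not successfully subside (i.e., falling below a 3 rating) after the secondary stimulation".

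Section 3.0 then refers the reader onward: "Each of these study dismissal criteria are described in more detail in the Procedures section (6.0), and detailed in the Appendix E flowchart". The flowchart is not in the text available for review. The SAP does not mention secondary CES.

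**The concern.** The trigger and the two definitions of subsiding all turn on the value 3, and the two definitions place that value on opposite sides. Staff who face a participant at exactly 3 in both sections can act in opposite ways and comply with the Protocol each time.

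Four things depend on the answer:

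- whether a second block is given;
- how many blocks are recorded as needed to resolve the symptoms;
- whether the session counts toward dismissal;
- what standard applies when the principal investigator inspects side-effect responses under Section 19.0 to confirm that staff follow the mitigation procedures.

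Dismissal is final for the data. Section 16.0 has the data of withdrawn participants destroyed and not analysed, in a trial that aims for 20 complete data sets per group (Section 5.2).

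**Working it through.** The plan gives no figure to reproduce. The check is logical, with a little arithmetic on device time.

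**Assumption.** Ratings are whole numbers from 1 to 4 in each section. The Protocol states that scale for the Daily Participant Questionnaire; the side-effects form is in an appendix that was not available. The result for 3/3 (a rating of 3 in both sections) needs only that 3 is a permitted rating.

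**Step 1: classify every pair for one item** (4 × 4 = 16 pairs of intensity and relation).

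| Pair | Meets trigger (both at least 3) | Subsided, Section 6.0 (all at most 3) | Subsided, Section 3.0 (below 3) |
|---|---|---|---|
| both 1 or 2 (4 pairs) | no | yes | yes |
| one 3, the other 1 or 2 (4 pairs) | no | yes | depends on reading |
| one 4, the other 1 or 2 (4 pairs) | no | no | depends on reading |
| 3/3 (1 pair) | yes | yes | no |
| 3/4, 4/3, 4/4 (3 pairs) | yes | no | no |

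The pairs sum to 4 + 4 + 4 + 1 + 3 = 16. Only 3/3 both meets the trigger and counts as subsided under Section 6.0. It fails Section 3.0 whether that wording means that every rating is below 3 or that the item is no longer at 3 or more in both sections. A participant who enters at 3/3 meets the Section 6.0 stopping definition before any secondary block is given.

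The third row is a second mismatch. The trigger needs both sections, but the stopping rule refers to all ratings. An item above 3 in one section and below 3 in the other is outside the trigger, yet it has not subsided under Section 6.0. The rows marked as depending on reading arise because Section 3.0 does not say which section its cutoff covers.

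**Step 2: follow a 3/3 as the worst rating.**

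- *After block 1.* Under Section 6.0, secondary CES ends: 20 + 5 = 25 minutes of device time, with 1 block recorded. If the Section 3.0 cutoff is applied to stopping, a second block follows: 20 + 5 + 5 = 30 minutes. The difference is 30 − 25 = 5 minutes. If the participant then falls below 3, both sections retain them, and only the blocks given and recorded differ.
- *After block 2, having been worse than 3/3 after block 1.* Both cutoffs give two blocks and 30 minutes. Only the status of the session for dismissal differs.
- *Stopping by Section 6.0, dismissing by Section 3.0.* A 3/3 after block 1 ends secondary CES as subsided and yet counts toward dismissal.
- *3/3 left when secondary CES ends, after either block, in two consecutive sessions.* Section 3.0 dismisses. Section 6.0 retains, if its definition carries into its own withdrawal sentence.

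**Step 3: check whether other text settles it.** In the example CES schedule, two blocks with their breaks take 2 × (5 + 1) = 12 minutes and fit the 15-minute slot from 0835 to 0850. The schedule is therefore compatible with either cutoff. The cross-reference from Section 3.0 leads to the section that holds the other definition.

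**The case against.** The best reply is that this is a narrow drafting slip. In Section 6.0 the cutoff is attached to repeating the blocks, and the dismissal sentence has none of its own. Section 3.0 is the only text that states a cutoff for dismissal, and Appendix E may state one too. The affected value is a single pair, and dismissal also requires the outcome to repeat in two consecutive sessions. Section 6.0 sets each participant's intensity 50 µA below the level that produced ratings of 3 or more in both sections, except for those who reach the maximum without such a rating. That should make such ratings less likely.

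Much of this stands. The conflict over dismissal depends on carrying the Section 6.0 definition forward to a sentence shortly after it in the same procedure. That is the natural reading, but it is an inference. The margin of 50 µA is relevant, although thresholding holds each step for 30 seconds while a session lasts 20 minutes, so it does not rule out a rating of 3. Appendix E could show which cutoff was meant, but Sections 3.0 and 6.0 would still disagree. The conflict over a second block, if the Section 3.0 meaning is applied to stopping, does not depend on the dismissal sentence.

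A reader might infer that the ambiguity biases the comparison of Active with Sham. The documents do not support that. Extra device time is extra current only in the Active arm, because for Sham devices "they do not actually send any electrical current to the electrodes". But nothing shows that 3/3 ratings, or dismissals for them, differ between arms. A reader might also derive a number of dismissals from the estimate in Section 15.0 of under 25% for side effects. That figure covers side effects in general, has no stated unit (participants or sessions), and does not concern ratings left after secondary CES.

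**Conclusion.** The inconsistency is real and lies in operative text: at 3/3 the trigger is still met, Section 6.0 says subsided and Section 3.0 says not subsided. The mismatch between a trigger on both sections and a stopping rule on all ratings is a further gap in the same procedure.

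Its size is limited. The 5-minute difference arises only for a 3/3 after the first block. The difference in dismissal needs 3/3 as the worst remaining rating in two consecutive sessions, and on the Section 6.0 side it rests on the inference described above. How often either occurs cannot be estimated from the documents. Destruction of withdrawn participants' data is a separate rule that raises the cost of a wrong dismissal; this cutoff does not cause it. The point should be fixed because it decides exposure and retention, but it is not evidence against the planned analysis.

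**What to change.** Reconcile the fifth criterion in Section 3.0 with the trigger, stopping and withdrawal text in Section 6.0, and check the Appendix E flowchart against them. The three rules should share one mutually exclusive cutoff, so that no rating both meets the trigger and counts as subsided. The text should state which questionnaire section or sections the cutoff covers. The investigators decide the cutoff; this review takes no position on it. The reconciled rule then serves as the standard for the Section 19.0 inspection.

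If sessions have already been run, state which rule staff applied and, where records exist, report dismissals under the fifth criterion by arm. Section 16.0 may mean that the ratings of dismissed participants no longer exist.

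The cost is a short protocol amendment through the IRB of record, communicated to the second oversight office as Section 23.0 requires, and a notice to staff. The count by arm, where possible, is a small addition. Sample size and analysis model do not change.
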